7. GENERAL CONSIDERATIONS

7.1. REFERENCE START DATE AND STUDY DAY

Study Day (or Start and End Study Day) will be calculated from the reference start date, and will be used to show start/ stop day of assessments and events.

Reference start date is defined as the day of the first dose of study medication in this study, (Day 1 is the day of the first dose of study medication), and will appear in every listing where an assessment date or event date appears.

- Study Day = (date of event – reference date) +1, (if event date \geq reference date)
- Study Day = date of event – reference date, (if event date is $<$ Day 1)

In the situation where the event date is partial or missing, Study Day, and any corresponding durations will appear partial or missing in the listings.

7.2. BASELINE

During the subjects transition from their previous study into AT1001-042, the intent is for treatment with migalastat HCl to continue without a drug holiday. Assessments collected in the last treatment visit of their previous study

Document: \\quintiles.net\enterprise\Sites\CAMTL\IntProjects\SasData\Amicus\AT1001\AXA23225A\Biostatistics\Documentation\SAP\DR\Amicus_AT1001-042_SAP_Final_v1.0_20190821.docx

Author: Amicus

Version Number: Final v1.0

Version Date: 21AUG2019

Template No.: CS_TP_BS016 Revision 5

Reference: CS_WI_BS005

Effective Date: 01Apr2018

(previous studies include AT1001-012 and AT1001-041), are also required for the Baseline Visit in the current study, which will serve as the assessment for the Baseline Visit. The visit window for the last treatment visit in the previous study will also apply to those Baseline assessments. However, to provide flexibility to investigators and subjects, any Baseline Visit assessment that are required for the current study and not a required assessment for the last treatment visit in the previous study, may be performed up to 30 days after entry into the current study. The baseline will then be determined as the last non-missing measurement taken prior to the first migalastat dose date (including unscheduled assessments) during this study. Should there be no observations prior to the first dose, the baseline will then be assigned to the observation at the nominal baseline visit.

Blood and urine sampling for plasma migalastat determination will be taken just prior to dosing and at selected time points post-dose.

Use of ACEi/ARB/RI at baseline is defined as having either ACE inhibitor, ARB or RENIN inhibitor within the past five years (with start date on or before the baseline visit) and is ongoing through, or the stop day is on or after the baseline visit date (informed consent date).

7.3. RETESTS, UNSCHEDULED VISITS AND EARLY TERMINATION DATA

In general, for by-visit summaries, data recorded at the nominal visit will be presented. Unscheduled measurements will not be included in by-visit summaries but will be included in tables presenting the clinically significant (CS) evaluations at any time of the study. All visits, including nominal, unscheduled, retest, and early termination visits will be sorted and presented chronologically. The visit wording to be presented in all outputs can be referred in Appendix 1.

In the case of a retest (same visit number assigned but tested on different dates), the first available measurement for that visit will be used for by-visit summaries.

Listings will include scheduled, unscheduled, retest and early discontinuation data.

7.4. WINDOWING CONVENTIONS

No visit windowing will be performed for this study.

Document: \\quintiles.net\enterprise\Sites\CAMTL\IntProjects\SasData\Amicus\AT1001\AXA23225A\Biostatistics\Documentation\SAP\DR\Amicus_AT1001-042_SAP_Final_v1.0_20190821.docx

Author: Amicus

Version Number: Final v1.0

Version Date: 21AUG2019

Template No.: CS_TP_BS016 Revision 5

Reference: CS_WI_BS005

Effective Date: 01Apr2018

7.5. STATISTICAL TESTS

There will be no formal inferential statistics performed in this study and only descriptive statistics will be presented.

7.6. COMMON CALCULATIONS

For quantitative measurements, change from baseline will be calculated as:

- Change from Baseline = Test value at Visit X – Baseline Value
- Continuous variables (e.g., age) are summarized using descriptive statistics (the number of subjects with available data, mean, standard deviation [SD], median, minimum, and maximum). Categorical variables (e.g., gender) are summarized using counts and percentages. Percentages are calculated using the total subjects (per population).
- For continuous variables, all mean and median values are formatted to one more decimal place than the measured value. SD values are formatted to two more decimal places than the measured value. The minimum and maximum values are presented with the same number of decimal places as the measured value.
- For categorical variables, the number and percentage of responses are presented in the form XX (XX.X%) where the percentage is in the parentheses. In case of 0 counts, only “0” with no percentage will be presented and a percentage of 100 will not include decimals, e.g. 85 (100%).

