6.2. INTENT-TO-TREAT [ITT]

The Intent-to-Treat (ITT) Population will include subjects who take at least one dose of Investigational Product (IP) after they have enrolled into this open-label extension study (excluding addendum 1.1.2 subject), and is the primary population of interest. All safety, efficacy and demography summaries will be based on the ITT population. Protocol

Document: \\quintiles.net\enterprise\Sites\CAMTL\IntProjects\SasData\Amicus\AT1001\AXA23225A\Biostatistics\Documentation\SAP\DR\Amicus_AT1001-042_SAP_Final_v1.0_20190821.docx

Author: Amicus

Version Number: Final v1.0

Version Date: 21AUG2019

Template No.: CS_TP_BS016 Revision 5

Reference: CS_WI_BS005

Effective Date: 01Apr2018

deviations will be reported in a listing.

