18. SAFETY OUTCOMES

The safety parameters include Adverse Events, Physical Examination, Vital Signs, Laboratory Tests, 12 Lead ECG, use of Concomitant Medications. All outputs for safety outcomes will be based on the ITT population using nominal visits (not including unscheduled visits and early termination) except tables presenting clinically significant results. These tables presenting clinically significant results will include unscheduled visits and early termination alongside the scheduled visits. Each continuous variable will be summarized for quantitative analysis using descriptive statistics by each visit including baseline, and change from baseline for that visit. Categorical variables will be summarized for qualitative analysis using incidence counts and percentages. The summary will be performed by each visit including baseline for each categorical parameter (e.g. Urinalysis parameters except pH and specific gravity).

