18.4.1. LABORATORY REFERENCE RANGES AND CLINICAL SIGNIFICANCE

Quantitative laboratory measurements will be compared with the relevant laboratory reference ranges in SI units and categorized as:

- Low: Below the lower limit of the laboratory reference range.
- Normal: Within the laboratory reference range (upper and lower limit included).
- High: Above the upper limit of the laboratory reference range.

For reference range with a single boundary, there will be only two of the three categories presented for the parameter (either Low/Normal, or Normal/High), e.g. Magnesium concentration is deemed High if result > 1.25 mmol/L, and Normal if at or below 1.25 mmol/L.

For categorical results in Urinalysis, they will be categorized into two categories, i.e. Normal/Abnormal if the result is different from that of the normal reference value. Shifts from baseline to any post-baseline visit summary tables based on the Low/Normal/High categories (and the variants) described above will be provided.

In addition to the high and low quantitative laboratory assignments, any result deemed clinically significant by the PI will be captured in the eCRF, and will be presented in the summary tables.

Document: \\quintiles.net\enterprise\Sites\CAMTL\IntProjects\SasData\Amicus\AT1001\AXA23225A\Biostatistics\Documentation\SAP\DR\Amicus_AT1001-042_SAP_Final_v1.0_20190821.docx

Author: Amicus

Version Number: Final v1.0

Version Date: 21AUG2019

Template No.: CS_TP_BS016 Revision 5

Reference: CS_WI_BS005

Effective Date: 01Apr2018

18.5. 12 LEAD ECG (ECG) EVALUATIONS

Results from the central ECG (Electrocardiogram) Reading Centre will be included in the reporting of this study. The following ECG parameters will be reported in summary tables using descriptive statistics for this study:

- PR Interval (msec)
- QRS Interval (msec)
- QT Interval (msec)
- QTcF Interval (msec)
- HR (bpm)
- RR (msec)

All findings, including clinically significant findings, will be captured by the eCRF for the overall ECG evaluation, and categorized into Normal; Abnormal, NCS; and Abnormal, CS.

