18.6. ECHOCARDIOGRAPHY (ECHO)

ECHO parameters are categorized into Normal, Mildly Abnormal, Moderately Abnormal, Severely Abnormal (or Low, Normal, High) by gender (or age) based on the criteria below for safety purpose, and a table presenting counts and percentages of each category by parameter and visit will be provided. A table presenting Severely Abnormal incidence at any visits through the study including unscheduled visits will be included.

ECHO Parameters	Criteria for Female	Criteria for Male	Abnormality Category
Left Ventricular Posterior Wall Thickness Diastole (cm) (LVPWTD)	0.6 - 0.9	0.6 - 1.0	Normal
	1.0 - 1.2	1.1 - 1.3	Mildly Abnormal

Document: \\quintiles.net\enterprise\Sites\CAMTL\IntProjects\SasData\Amicus\AT1001\AXA23225A\Biostatistics\Documentation\SAP\DR\Amicus_AT1001-042_SAP_Final_v1.0_20190821.docx

Author: Amicus

Version Number: Final v1.0

Version Date: 21AUG2019

Template No.: CS_TP_BS016 Revision 5

Reference: CS_WI_BS005

Effective Date: 01Apr2018

ECHO Parameters	Criteria for Female	Criteria for Male	Abnormality Category
	1.3 - 1.5	1.4 - 1.6	Moderately Abnormal
	≥ 1.6	≥ 1.7	Severely Abnormal
Intraventricular Septum Thickness Diastolic (cm) (IVSTD)	0.6 - 0.9	0.6 - 1.0	Normal
	1.0 - 1.2	1.1 - 1.3	Mildly Abnormal
	1.3 - 1.5	1.4 - 1.6	Moderately Abnormal
	≥ 1.6	≥ 1.7	Severely Abnormal
Left Ventricular Ejection Fraction (%) (LVEF)	≥ 55	Same as female	Normal
	45 - 54	Same as female	Mildly Abnormal
	30 - 44	Same as female	Moderately Abnormal
	< 30	Same as female	Severely Abnormal
Fractional Shortening (%) (FS)	27 - 45	25 - 43	Normal
	22 - 26	20 - 24	Mildly Abnormal
	17 - 21	15 - 19	Moderately Abnormal
	≤ 16	≤ 14	Severely Abnormal
Left Ventricular Mass (g) (LVM)	67 - 162	88 - 224	Normal
	163 - 186	225 - 258	Mildly Abnormal
	187 - 210	259 - 292	Moderately Abnormal
	≥ 211	≥ 293	Severely Abnormal
Left Ventricular Mass Index (g/m ²) (LVMI)	43 - 95	49 - 115	Normal

Document: \\quintiles.net\enterprise\Sites\CAMTL\IntProjects\SasData\Amicus\AT1001\AXA23225A\Biostatistics\Documentation\SAP\DR\Amicus_AT1001-042_SAP_Final_v1.0_20190821.docx

Author: Amicus

Version Number: Final v1.0

Version Date: 21AUG2019

Template No.: CS_TP_BS016 Revision 5

Reference: CS_WI_BS005

Effective Date: 01Apr2018

ECHO Parameters	Criteria for Female	Criteria for Male	Abnormality Category
	96 - 108	116 - 131	Mildly Abnormal
	109 - 121	132 - 148	Moderately Abnormal
	≥ 122	≥ 149	Severely Abnormal

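### SAP 7.6 sets the ITT total as denominator for all percentages, with no by-visit exception, so by-visit urinalysis and ECHO category percentages shrink as fewer subjects are assessed

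*SAP*

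**What the plan says.** SAP 7.6 treats the two kinds of variable differently. For continuous variables the reported n is "the number of subjects with available data". For categorical variables the rule is "Percentages are calculated using the total subjects (per population". The same section has each count printed with its percentage in parentheses.

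The population is fixed in SAP 6.2: "All safety, efficacy and demography summaries will be based on the ITT population". SAP 18 repeats this for safety and limits the data used: "All outputs for safety outcomes will be based on the ITT population using nominal visits (not including unscheduled visits and early termination"), with an exception only for tables of clinically significant results.

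Two sets of by-visit categorical percentages are planned:

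- **Urinalysis.** SAP 18 says "Categorical variables will be summarized for qualitative analysis using incidence counts and percentages" and "The summary will be performed by each visit including baseline for each categorical parameter", with urinalysis as its example. SAP 18.4.1 says of categorical urinalysis results that "they will be categorized into two categories, i.e. Normal/Abnormal".
- **ECHO.** SAP 18.6 says "a table presenting counts and percentages of each category by parameter and visit will be provided".

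Neither section states its own denominator. SAP 8.3 rules out imputation. SAP 9 leaves the format and content of tables to templates, which are not among the documents reviewed.

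**The concern.** The number of subjects with a result can be expected to fall below the ITT total at later visits. Treatment duration differs between subjects (SAP 4.1), the protocol requires withdrawal when a stopping criterion is met (Protocol 8.2.2), and exposure is tabulated in bands up to 48 months (SAP 15). By-visit tables also leave out unscheduled and early-termination results. A subject with no result at a nominal visit stays in that visit's denominator but cannot be counted in any category there.

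The ECHO schedule may add a shortfall of its own. The End of Study ECHO is for withdrawing subjects who had none in the preceding 6 months (footnote 3 to the Time and Events table), yet End of Study is a listed output visit (SAP Appendix 1). If that row is tabulated for ECHO, subjects who were not due a scan still count in its denominator.

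Long-term safety is the primary objective and the study is descriptive, so the printed percentages are themselves the result. A percentage that mixes the abnormality rate with attendance is hard to read across visits.

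**Working it through.** The plan states no by-visit n, retention figure or by-visit percentage, so there is nothing of its own to reproduce. The check is an identity, followed by illustrations on assumed values.

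**Inputs from the documents**
- Denominator: all subjects in the population (SAP 7.6), which is ITT for safety (SAP 6.2 and 18).
- Expected enrolment: up to 100 (Protocol 6.1), used only as the illustrative N.
- Missing results: not imputed (SAP 8.3).

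**Assumed:** the number assessed at each visit, and the abnormality rates.

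**Formula.** Let x be the count in a category, n the number assessed at the visit and N the ITT total.

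- Printed percentage = x/N = (x/n) × (n/N).
- Sum over exhaustive categories = n/N, not 100%.

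**Constant rate, any N.** Suppose 25% of those assessed are abnormal at every visit:

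| n/N | Calculation | Printed |
|---|---|---|
| 100% | 25% × 1.0 | 25.0% |
| 90% | 25% × 0.9 | 22.5% |
| 70% | 25% × 0.7 | 17.5% |
| 50% | 25% × 0.5 | 12.5% |

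**Rising rate, assumed N = 100.** Baseline is 20/100 = 20.0%.

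- Later visit, 80 assessed, 24 abnormal: 24/80 = 30.0% among those assessed, but 24/100 = 24.0% is printed. The rise is understated.
- Later visit, 50 assessed, 15 abnormal: 15/50 = 30.0% among those assessed, but 15/100 = 15.0% is printed. The rise appears as a fall.

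**Break-even.** A rise from 20% to 30% prints as flat when 30% × n/N = 20%, so n/N = 20/30 = 66.7%. Below that it prints as a fall.

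**A series of visits, assumed N = 100.** With n of 100, 80, 60, 40 and 20, and rates among those assessed of 20%, 25%, 30%, 40% and 60%, the printed figures are 20.0%, 20.0%, 18.0%, 16.0% and 12.0%.

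**Can the reader recover n?** Often, because counts are printed. In the 50-assessed example, a two-way urinalysis table shows 15 abnormal (15.0%) and 35 normal (35.0%). The counts sum to n = 50, and 15/50 returns 30.0%. This needs categories that cover every possible value. For LVIDs, SAP 18.6 gives only a normal range, so a subject outside it and a subject not assessed look alike in that table.

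**The case against.** The case on the other side has real weight.

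- **The templates may already use visit n or show a Missing row.** This stands. A reader might infer that the final tables will be wrong; the documents do not establish that. If the templates are right, they conflict with 7.6 as worded and only the SAP sentence needs changing.
- **The example variable in 7.6 is gender, so one-time variables may have been meant.** Possible, but the rule sits under common calculations and carries no such limit.
- **Counts allow the rate to be recovered.** This largely stands and lowers the severity. It fails within the LVIDs category table, where n would have to be sought elsewhere, such as the continuous ECHO summary.
- **Change over time is shown elsewhere on available data.** This stands. The main ECHO measures (SAP 17.1.6) and continuous laboratory, vital-sign and ECG values are summarised by visit with available n. It is tempting to conclude that the plan would hide a safety trend; with these tables present, that goes too far.
- **ITT N is right for incidence tables.** This stands. Adverse events and findings at any time on study belong on ITT N, so a reading that all safety percentages are understated is not supported.
- **Shift tables.** The laboratory and ECG shift sentences (SAP 18.4.1 and 18.5) state no percentages, and the laboratory one does not clearly describe a table for each visit. They are affected only if they print percentages by visit.
- **The rate among those assessed is not the true rate.** This stands. Mandatory withdrawal for worsening can remove abnormal subjects, so a visit-n percentage is open to selective dropout. It is easier to interpret, but it is not an unbiased estimate for the whole cohort.

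**Conclusion.** The point holds for the by-visit urinalysis and ECHO category tables. As 7.6 is worded, their percentages equal the percentage among those assessed multiplied by n assessed / N ITT. That factor is 1 where every subject is assessed and falls in step with attendance. The scaling is exact. Its size in this study cannot be known from the documents, because N, n and the abnormality rates above are all assumed; the illustrated reversal shows what the rule permits, not what will happen.

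The conclusion rests on the protocol and SAP text available, some of which is missing, and on no template overriding 7.6. Severity is minor to moderate: a stated rule that does not suit these tables, partly offset by printed counts and by the continuous summaries. All analyses are descriptive (SAP 7.5), so no test or sample size is touched.

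**What to change.** - **SAP 7.6.** State that by-visit percentages use the number of subjects with a non-missing result at that visit, and that this n is displayed. For any by-visit shift table, require a result at both baseline and that visit. Alternatively, keep ITT N and add a Missing row at each visit; in the example, 15 abnormal and 50 missing lets the reader compute 15/(100 − 50) = 30.0%.
- **Leave adverse event and any-time tables on ITT N.**
- **Templates.** Check them against the revised sentence and align them.
- **Footnote.** Say on by-visit categorical tables that later visits describe only subjects still assessed, a group subject to selective withdrawal.

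The cost is one SAP sentence, an n line or Missing row, and a footnote. No new data are needed. If the templates already use visit n, the denominator change is confined to the SAP sentence.

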7.7. SOFTWARE VERSION

All analyses will be conducted using SAS version 9.2 and above.

8. STATISTICAL CONSIDERATIONS

8.1. ADJUSTMENTS FOR COVARIATES AND FACTORS TO BE INCLUDED IN ANALYSES

Since there are no formal inferential statistics performed, no analysis will be adjusted for covariates or factors.

Document: \\quintiles.net\enterprise\Sites\CAMTL\IntProjects\SasData\Amicus\AT1001\AXA23225A\Biostatistics\Documentation\SAP\DR\Amicus_AT1001-042_SAP_Final_v1.0_20190821.docx

Author: Amicus

Version Number: Final v1.0

Version Date: 21AUG2019

Template No.: CS_TP_BS016 Revision 5

Reference: CS_WI_BS005

Effective Date: 01Apr2018

8.2. MULTICENTRE STUDIES

This study will be conducted by multiple investigators at multiple centers internationally, but no site-specific considerations will be included in the analysis, and data from all sites will be pooled in the analysis.

8.3. MISSING DATA

No missing data imputation will be carried out in this study.

8.4. MULTIPLE COMPARISONS/ MULTIPLICITY

No adjustment for multiplicity will be performed. All analyses will be descriptive.

8.5. EXAMINATION OF SUBGROUPS

Descriptive analyses of the efficacy endpoints (annualized change in MDRD eGFR and CKD-EPI eGFR) will be performed on the following subgroups:

- Males, 24-hr urine protein < 100 mg/24h
- Males, 24-hr urine protein ≥ 100 , <1000 mg/24h
- Males, 24-hr urine protein ≥ 1000 mg/24h
- Females, 24-hr urine protein < 100 mg/24h
- Females, 24-hr urine protein ≥ 100 , <1000 mg/24h
- Females, 24-hr urine protein ≥ 1000 mg/24h

9. OUTPUT PRESENTATIONS

Appendix 1 shows conventions for presentation of data in outputs.

The templates provided with this SAP describes the presentations for this study as well as format and content of the summary tables, figures, and listings to be provided by IQVIA Biostatistics.

Document: \\quintiles.net\enterprise\Sites\CAMTL\IntProjects\SasData\Amicus\AT1001\AXA23225A\Biostatistics\Documentation\SAP\DR\Amicus_AT1001-042_SAP_Final_v1.0_20190821.docx

Author: Amicus

Version Number: Final v1.0

Version Date: 21AUG2019

Template No.: CS_TP_BS016 Revision 5

Reference: CS_WI_BS005

Effective Date: 01Apr2018

10. DISPOSITION AND WITHDRAWALS

All subjects who provide informed consent will be accounted for in this study. Number of subjects, subject discontinuation, and primary reason for discontinuation will be presented for the ITT and Addendum 1.1.2 population.

The list of primary reasons for discontinuation (as per CRF) can be referred to as below:

- Screen Failure
- Adverse Event
- Subject Met Protocol Defined Stopping Criteria
- Physician Decision
- Lost to Follow-up
- Non-Compliance with Study Requirements
- Pregnancy and/or Breast feeding
- Protocol Violation
- Withdrawal by Subject
- Study Terminated by Sponsor
- Death
- Other

11. PROTOCOL DEVIATIONS

Protocol Deviations as classified in the clinical trial management system (CTMS) will be summarized in a table according to the following categories and presented overall based on the ITT population:

- Administrative Criteria
- Concomitant Medications Criteria
- Efficacy Criteria
- Eligibility and Entry Criteria
- Investigational Product Compliance
- Informed Consent Criteria
- Laboratory Assessment Criteria
- Randomization Criteria
- Regulatory or Ethics Approvals Criteria

Document: \\quintiles.net\enterprise\Sites\CAMTL\IntProjects\SasData\Amicus\AT1001\AXA23225A\Biostatistics\Documentation\SAP\DR\Amicus_AT1001-042_SAP_Final_v1.0_20190821.docx

Author: Amicus

Version Number: Final v1.0

Version Date: 21AUG2019

Template No.: CS_TP_BS016 Revision 5

Reference: CS_WI_BS005

Effective Date: 01Apr2018

- Serious adverse event (SAE) Criteria
- Source Document Criteria
- Study Procedures Criteria
- Visit Scheduled Criteria
- Other Criteria

All protocol deviations will be listed.

12. DEMOGRAPHIC AND OTHER BASELINE CHARACTERISTICS

Demographic data and other baseline characteristics will be presented for the ITT population. The following demographic and other baseline characteristics will be summarized using descriptive statistics under AT1001 (Migalastat HC1) column:

- Age (years) (calculated relative to date of consent)
- Sex
- Race
- Ethnicity (USA and Japan Sites only)
- Country
- Protocol Version
- Weight (kg)
- Height (cm)
- BMI (kg/m²)
- Use of angiotensin-converting enzyme inhibitors (ACEi)/angiotensin II receptor blockers (ARB)/renin inhibitors (RI)
- 24-hour urine protein (mg/24h)
- Estimated Glomerular Filtration Rate based on Chronic Kidney Disease Epidemiology Collaboration (eGFR_{CKD-EPI}) (mL/min/1.73m²)
- Estimated Glomerular Filtration Rate based on Modification of Diet in Renal Disease (eGFR_{MDRD}) (mL/min/1.73m²)
- Previous Studies (subjects can be in more than one previous study)

It will be considered use of ACEi/ARB/RI if the reported medication is taken on the date of consent, regardless of the start or end date.

Document: \\quintiles.net\enterprise\Sites\CAMTL\IntProjects\SasData\Amicus\AT1001\AXA23225A\Biostatistics\Documentation\SAP\DR\Amicus_AT1001-042_SAP_Final_v1.0_20190821.docx

Author: Amicus

Version Number: Final v1.0

Version Date: 21AUG2019

Template No.: CS_TP_BS016 Revision 5

Reference: CS_WI_BS005

Effective Date: 01Apr2018

eGFR_{MDRD} data will be calculated by the central lab and included in the data transfer, whereas eGFR_{CKD-EPI} data will be derived from serum creatinine based on the formula in Section 17.1.2.

Some of the baseline characteristics will not be collected directly in the eCRF and will be derived as follows:

- Age = (date of consent – date of birth) / 365.25. If date of birth contains only partial date, use the first day of the month in the calculation if day part is missing, or first day of the year if both day and month parts are missing.
- BMI (kg/m²) = weight (kg)/ height (m)² at the baseline visit

Demographic and baseline characteristics will be provided in two separate data listings.

